**Figure 5.a Schematic of Study Design**

## **5.2 Justification for Study Design, Dose, and Endpoints**

The question to be answered scientifically by this investigation is whether or not a new innovative, patented mixture of FDA approved antigens provides unequivocal superior clinical benefit in the symptomatic relief of individuals manifesting active SAR/PAR. Since extensive prior experience of managing patients with these medical conditions has demonstrated remarkable benefit from the immunotherapy technique within 3 to 6 weeks, the selection of study subjects and the overall study design can be scientifically justified.

The dose of immunotherapy, which will be administered sub-cutaneously bi-weekly for 8 weeks, will be the same for all subjects and will begin with vial number #5 which will be prepared by serial five fold dilutions from the most concentrated vial (#1).

The study sample size is based upon the results of prior immunotherapy investigations undertaken by the Investigators of this study and their colleagues in the Division of Allergy & Clinical Immunology, Johns Hopkins University School of Medicine. Efficacy for immunotherapy was

estimated to be 80% for treatment group and 30% for placebo. Using an error rate ( $\alpha$ ) of 0.05 and 80% Power we calculate a total sample size needed of 28 subjects. To account for drop off we will recruit up to 36 subjects.

### **5.3 Premature Termination or Suspension of Study or Investigational Site**

This study may be terminated at any time by the investigators or the sponsor for safety reasons or for just cause.

#### **5.3.1 Criteria for Premature Termination or Suspension of the Study**

The study will be completed as planned unless one or more of the following criteria are satisfied that require temporary suspension or early termination of the study.

- New information or other evaluation regarding the safety or efficacy of the study medication that indicates a change in the known risk/benefit profile for the immunotherapy, such that the risk or benefit is no longer acceptable for subjects participating in the study.
- Significant violation of Good Clinical Practice (GCP) that compromises the ability to achieve the primary study objectives or compromises subject safety.

#### **5.3.2 Criteria for Premature Termination or Suspension of the Investigational Site**

The study site may be terminated prematurely or suspended if the site is found in significant violation of GCP, protocol, or contractual agreement, is unable to ensure adequate performance of the study, or as otherwise permitted by the contractual agreement.

#### **5.3.3 Procedures for Premature Termination or Suspension of the Study or the Participation of the Investigational Site**

In the event that the sponsor, the institutional review board or regulatory authority elects to terminate or suspend the study or the participation of the investigational site, a study-specific procedure for early termination or suspension will be provided by the sponsor; the procedure will be followed by the investigational site during the course of termination or study suspension.

---

## **6.0 SELECTION AND DISCONTINUATION/WITHDRAWAL OF SUBJECTS**

All entry criteria, including test results, need to be confirmed prior to the administration of first dose of immunotherapy.

### **6.1 Inclusion Criteria**

1. In the opinion of the investigator, the subject is capable of understanding and complying with protocol requirements.
2. The subject signs and dates a written, informed consent form prior to the initiation of any study procedures.
3. The subject is a male or a non-pregnant, non-lactating female between the ages of 18 and 65.
4. The study subject is currently experiencing active symptoms and signs of moderate to severe PAR with or without SAR component defined as score of at least 28 on the RQLQ and 6 on the TNSS scale. Scores will be determined on the first and second visit (after the 14 day medication washout period). Both scores exceeding their threshold on either day will qualify.
5. Skin test strongly positive (wheal at least 5mm diameter and 2mm greater than negative control) to at least 6 of 48 allergy skin prick tests including at least one species of dust mite.

### **6.2 Exclusion Criteria**

Any subject who meets any of the following criteria will not qualify for entry into the study:

1. The subject has received any investigational compound within 30 days prior to screening.
2. The subject has received multi antigen immunotherapy or SLIT in a previous clinical study or as a therapeutic agent within the past two years.
3. The subject has a history or clinical manifestations of significant medical conditions (cardiovascular, hepatic, infectious or renal disease, etc.) which in the opinion of the investigator renders them unacceptable study subjects.
4. The subject has a history of drug abuse (defined as any chronic illicit drug use) or a history of alcohol abuse within 5 years prior to the screening visit.
5. The subject is required to take excluded medications listed in Section 6.3.
6. If female, the subject is pregnant or lactating or intending to become pregnant before, during, or within 1 month after participating in this study; or intending to donate ova during such time period.
7. Subjects found to have on physical exam significant nasal polyps, septal deviation or infectious sinusitis.

### **6.3 Excluded Medications**

- Immunotherapy that is not part of the investigation
- Beta2 agonists and angiotensin converting enzyme (ACE) inhibitors
- Other medications that may interfere with the test, analysis, or interpretation of results.
- Omalizumab and other anti-asthma biologics, or immune suppression treatment within 6 months of participating in the investigation, including oral corticosteroids within the month.
- Subjects must be instructed not to take any medications including over-the-counter products, without first consulting with the investigator.

Note that prior use of medications commonly used to treat allergic rhinitis such as nasal steroids, antihistamines, ophthalmologic antihistamines, cromolyn, azelastine, decongestants and other OTC allergy medications are not excluded. However, these medication will be stopped during the 14 day washout period. Patients are encouraged to abstain from using these medications for the duration of the study. If symptoms are not adequately controlled the rescue medications will be added in a stepwise fashion as outlined in section 12.1.3.

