### **6.4 Criteria for Discontinuation or Withdrawal of a Subject**

The primary reason for discontinuation or withdrawal of the subject from the study or study medication should be recorded in the CRF using the following categories. For screen failure subjects, refer to Section 8.1.11.

1. Pretreatment event (PTE) or adverse event (AE). The subject has experienced a PTE or AE that requires early termination because continued participation imposes an unacceptable risk to the subject's health or the subject is unwilling to continue because of the PTE or AE.
2. Significant protocol deviation. The discovery postrandomization or after the first dose of study immunotherapy that the subject failed to meet protocol entry criteria or did not adhere to protocol requirements, and continued participation poses an unacceptable risk to the subject's health.
3. Lost to follow-up. The subject did not return to the clinic and attempts to contact the subject were unsuccessful. Attempts to contact the subject must be documented.
4. Voluntary withdrawal. The subject (or subject's legally acceptable representative) wishes to withdraw from the study. The reason for withdrawal, if provided, should be recorded in the

CRF. All attempts should be made to determine the underlying reason for the withdrawal and, where possible, the primary underlying reason should be recorded.

5. Study termination. The sponsor, IRB, or regulatory agency terminates the study.
6. Pregnancy. The subject is found to be pregnant.

Note: If the subject is found to be pregnant, the subject must be withdrawn immediately. The procedure is described in Section 8.1.10.

7. The investigator has determined that continued participation would pose an unacceptable risk to the subject.

Note: After the 30 minute wait period, subjects that develop local swelling at the site of the injection greater than 50mm diameter will have their next dose decreased by one step. Subjects having a Grade 1-2 systemic reaction will have their next injection decreased by two steps. Systemic reaction Grade 3 or more will require withdrawal from the study. Systemic reactions are defined by the World Allergy Organization anaphylaxis grading system (13).

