#### *7.1.4 Immunotherapy Dose and Regimen*

Recruited subjects alternate to be assigned either treatment set I or II (representing either placebo or active PMA treatment in a binded fashion). The assigned treatment set will remain for the duration of the study for each subject. On the day of an injection, 0.3ml from each of the appropriate vial set mix (A-C) will be combined in a sterile 5 ml bottle. Using a new sterile syringe, 0.15-0.60ml of the PMA solution or placebo will be removed for injection purposes according to the injection schedule (Appendix I). A sterile 27G ½ inch syringe will be used for administration. Immunotherapy will be administered bi-weekly in the study clinic for a total of eight consecutive weeks. Appendix I lists the precise immunotherapy injection schedule.

All patients are required to remain in the clinic under close observation by the study nurse for a period of 30 minutes following their injection. A physician is required to be present in the clinic at all times. In addition, one of the investigators must be present on campus and available by cell phone during scheduled treatment sessions. Emergency medications such as albuterol, oxygen, diphenhydramine, and at least two epi-pens will be readily available in the treatment area.

It is important to note that the maximum concentration of each individual allergen is quite low compared to more traditional immunotherapy regimens. The maximum PNU/ml (Protein Nitrogen Units) in vial #1 will be no more than about 180 PNU/ml per allergen (eg 0.9ml of 20,000 PNU/ml stock material into 100ml solution). In most cases the actual concentration of each stock allergen is much lower than 20,000 PNU/ml since the material may be provided as a mixture of several allergens. We would estimate therefore that subjects would receive no more than about 7.2 PNU of antigen contained in the highest injection (0.2ml Vial #2). Typically, allergens are administered via immunotherapy in a range of about 2000 PNU. Thus the dosage of each allergen is less than 0.36% of a typical dose administered in our clinics. The lower overall dosing scheme provided in this study would therefore be considered to be extremely safe with minimal adverse events.

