### **14.2 Risks**

**Allergy Skin test** The risk of performing allergy skin testing is minimal. Serious reactions are rare. This study uses histamine and allergen for testing, which very rarely can cause serious reactions.

Most individuals experience mild to moderate itching at the site of testing that spontaneously resolves. You may feel some mild discomfort from the skin prick device itself.

**Immunotherapy** The most common side effect from allergen immunotherapy is slight swelling and discomfort at the site of the injection. This usually resolves in 1-2 days with the use of a cool pack. There is a very small chance of having a serious allergic reaction. If symptoms of a serious allergic reaction occur we would administer epinephrine and possibly other allergy medications such as antihistamines.

Some participants will receive placebo instead of active immunotherapy. These individuals may not see an improvement in their symptoms. All patients will be required to discontinue nasal steroids for two weeks prior to starting treatment. There is a risk that nasal symptoms could worsen when you stop the medication.

**Blood Draw** The most common side effect of blood draw is discomfort from the needle. This can sometimes lead to bruising of the skin. There is a very small chance of getting an infection from puncturing the skin.

**Other risks** There always exists the potential for loss of confidentiality; however, there are procedures in place to minimize this. Study information will not be associated with your private demographic information directly but linked via a numerical code only to be accessed by the study designers. However, there still remains the possibility that information about you may become known to people outside of this study.

You may get tired or bored when we are asking you questions or you are completing questionnaires. You do not have to answer any question you do not want to answer. There may be side effects and discomforts that are not yet known.

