## **Other Comparisons and Outcomes**

1. Baseline characteristics - Comparison of the rates of specific characteristics between both treatment groups I and II using a one-tailed Fischer's exact test and/or unpaired t test.
2. Use of epinephrine - Comparison of the rates of epinephrine rescue medication use between both treatment groups I and II using a one-tailed Fischer's exact test.
3. Mini-RQLQ - Kaplan-Meier or similar repeated measures test will also be used to calculate the effect of treatment over time between both groups I and II.
4. Drop out - Comparison of the drop out rates between both groups I and II using a one-tailed Fischer's exact test.
5. Trend tests - For these study data, representing a continuous response, an appropriate test, such as the Jonckheere-Terptsra trend test, based on a sum of Mann-Whitney-Wilcoxon tests may be sensitive and reveal a mild trend where pair-wise comparisons may not be able to find significant differences and not be as helpful. Other trend tests may also be used.

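### No exclusion names beta-blockers, although the plan relies on epinephrine and albuterol to treat injection reactions

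*Combined protocol and SAP*

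**What the plan says.** Section 6.3 bars some medications by class. The relevant line reads "Beta 2 agonists and angiotensin converting enzyme (ACE) inhibitors". Exclusion 5, in both 1.3 and 6.2, turns the list into an entry criterion: "The subject is required to take excluded medications listed in Section 6.3".

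The treatment of reactions appears in two places. Section 14.2 says "If symptoms of a serious allergic reaction occur we would administer epinephrine and possibly other allergy medications such as antihistamines". Section 7.1.4 says "Emergency medications such as albuterol, oxygen, diphenhydramine, and at least two epi-pens will be readily available in the treatment area".

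Appendix H schedules 16 injections, at visits 2 to 17, moving through four vials of rising strength. A mild systemic reaction does not end treatment; under 6.4, "Subjects having a Grade 1-2 systemic reaction will have their next injection decreased by two steps". The same note requires withdrawal at Grade 3 or above.

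Neither the protocol nor the SAP mentions beta-blockers.

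**The concern.** A trial that injects allergen into sensitised adults has to be able to treat a systemic reaction. The two adrenergic drugs the plan names, epinephrine and albuterol, act wholly or partly through beta receptors. A beta-blocker may weaken part of the response to each. That is general pharmacology; the documents do not say it.

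The plan already uses class-level bars, for example on ACE inhibitors, so leaving out beta-blockers is not explained by a preference for case-by-case judgement. As written, an adult taking a beta-blocker for a condition the investigator does not judge significant can be randomised and given the full series of injections. What is at stake is the safety of that subject if a serious reaction occurs. The scores, the analysis set and the conclusions are not affected.

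**Working it through.** The plan has no figure of its own on this point, so the check is first a reading of the text and then simple arithmetic on exposure.

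**1. Does any provision bar a beta-blocker user at entry?**

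- Exclusion 3 (6.2) covers "significant medical conditions (cardiovascular, hepatic, infectious or renal disease, etc.) which in the opinion of the investigator renders them unacceptable study subjects". It depends on the condition and on opinion, not on the drug.
- The general bullet in 6.3 covers "Other medications that may interfere with the test, analysis, or interpretation of results". A weaker response to emergency treatment is none of these.
- The last bullet of 6.3 has subjects consult the investigator before they take any medication. It calls for a conversation; it is not a bar.
- Section 8.3.1 takes medication history at screening, and 8.1.7 records concomitant drugs. Both would reveal a beta-blocker; neither acts on it.
- Section 8.3.3 leaves each injection to the investigator's judgement, and 6.4 item 7 allows withdrawal for unacceptable risk. Both are discretionary and apply after entry.
- Grade 3 withdrawal (6.4), and the 30-minute observation with a physician in the clinic (7.1.4), act once an injection has been given.

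None of these bars a beta-blocker user at entry.

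**2. How many users might enter?**

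Inputs: 36 subjects, 18 per arm (1:1 allocation, 5.1); 16 injections each (Appendix H). The rate of use p is not in the documents. I assume 1% to 5% of adults aged 18 to 65 who pass exclusion 3.

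Expected users = n × p. Chance of at least one = 1 − (1 − p)^n. Active injections given to users = 18 × 16 × p = 288p.

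| p | Users among 36 | At least one of 36 | Users among 18 active | At least one of 18 | Active injections to users |
|---|---|---|---|---|---|
| 1% | 0.36 | 30.4% | 0.18 | 16.5% | 2.9 |
| 3% | 1.08 | 66.6% | 0.54 | 42.2% | 8.6 |
| 5% | 1.80 | 84.2% | 0.90 | 60.3% | 14.4 |

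**3. How far is exposure from harm?**

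Harm also needs a serious reaction in a user. Section 9.1.4 reports none, and no need for epinephrine, in more than 20,000 patients. With zero events in 20,000, the approximate 95% upper bound is 3/20,000 = 0.00015 per patient. Multiplied by 0.18 to 0.90 active-arm users, this gives about 0.00003 to 0.00014 expected events per trial. It takes uncontrolled experience at face value and assumes users react at the same rate as others, so it is indicative only.

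The low dose points the same way. Section 7.1.4's figure reproduces: 0.9 ml × 20,000 PNU/ml ÷ 100 ml = 180 PNU/ml in vial #1; ÷ 5 = 36 in vial #2; × 0.2 ml = 7.2 PNU; ÷ 2,000 = 0.36% of a typical dose. Many candidate stocks in Appendix E are 40,000 PNU/ml, which would double this to 14.4 PNU, or 0.72%. That is still low, and 7.1.4 expects most actual concentrations to be well below its assumption.

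**The case against.** The strongest reply is that the risk is remote and already managed in layers. Each allergen dose is small, the reported experience contains no serious reaction, and a nurse observes each subject with a physician in the clinic and an investigator on campus. Oxygen and diphenhydramine are stocked as well. Epinephrine also acts through alpha receptors and beta-blockers differ in selectivity, so the loss of response would be partial.

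Much of this stands. For a subject who starts a beta-blocker during the study, the consultation rule in 6.3 and the investigator's decision at each injection in 8.3.3 already supply most of what is needed. What they leave open is entry: these safeguards rest on judgement, and no text tells the investigator that this class matters. A low dose lowers the chance of a reaction but does not improve the response to treatment if one occurs.

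Two stronger readings are tempting. A reader might infer that 6.3, by barring beta2 agonists, conflicts with stocking albuterol. It does not: through exclusion 5 the list limits what subjects themselves take, and it does not restrict what clinic staff give in an emergency. A reader might also infer that the beta2-agonist entry is a slip for beta-blockers, given its pairing with ACE inhibitors. That is possible, but the bar may equally be deliberate, for example to keep out treated asthma, since the same list bars anti-asthma biologics. The documents do not show which, and the omission stands either way.

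**Conclusion.** The point holds as a modest one about subject safety. No provision bars a beta-blocker user at entry, and the plan relies on two drugs whose effect a beta-blocker may partly blunt. The existing safeguards reduce the risk without closing that gap.

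The size depends on an assumed 1% to 5% rate of use, for which the documents offer no support. A reader might take the 30% to 84% as a risk of harm. It is only the chance that at least one user is enrolled among 36; the corresponding chance in the active arm is 17% to 60%. Serious reactions are expected to be very rare, so the expected harm in this trial is very small. The case for acting is that the remedy is nearly free.

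**What to change.** Add beta-blockers to the list in 6.3, so that exclusion 5 applies to them. Check for them in the medication history already taken at screening (8.3.1). State that a subject who starts one on study receives no further injection until the investigator has reviewed it. If the beta2-agonist entry was meant to read beta-blockers, correct the word; otherwise leave it as it is. State also that no subject should stop a prescribed beta-blocker in order to enter.

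The cost is one added drug class and a sentence or two in the protocol. At the assumed 1% to 5% rate, about 0.4 to 1.8 of 36 subjects would have to be replaced at screening (36 × 0.01 to 36 × 0.05). Sample size, visits and analysis do not change.

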### **6.4 Criteria for Discontinuation or Withdrawal of a Subject**

The primary reason for discontinuation or withdrawal of the subject from the study or study medication should be recorded in the CRF using the following categories. For screen failure subjects, refer to Section 8.1.11.

1. Pretreatment event (PTE) or adverse event (AE). The subject has experienced a PTE or AE that requires early termination because continued participation imposes an unacceptable risk to the subject's health or the subject is unwilling to continue because of the PTE or AE.
2. Significant protocol deviation. The discovery postrandomization or after the first dose of study immunotherapy that the subject failed to meet protocol entry criteria or did not adhere to protocol requirements, and continued participation poses an unacceptable risk to the subject's health.
3. Lost to follow-up. The subject did not return to the clinic and attempts to contact the subject were unsuccessful. Attempts to contact the subject must be documented.
4. Voluntary withdrawal. The subject (or subject's legally acceptable representative) wishes to withdraw from the study. The reason for withdrawal, if provided, should be recorded in the

CRF. All attempts should be made to determine the underlying reason for the withdrawal and, where possible, the primary underlying reason should be recorded.

5. Study termination. The sponsor, IRB, or regulatory agency terminates the study.
6. Pregnancy. The subject is found to be pregnant.

Note: If the subject is found to be pregnant, the subject must be withdrawn immediately. The procedure is described in Section 8.1.10.

7. The investigator has determined that continued participation would pose an unacceptable risk to the subject.

Note: After the 30 minute wait period, subjects that develop local swelling at the site of the injection greater than 50mm diameter will have their next dose decreased by one step. Subjects having a Grade 1-2 systemic reaction will have their next injection decreased by two steps. Systemic reaction Grade 3 or more will require withdrawal from the study. Systemic reactions are defined by the World Allergy Organization anaphylaxis grading system (13).

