### **Statistical Considerations:**

### **Efficacy Analyses**

The intent-to-treat approach will be used. Baseline characteristics (those collected prior to randomization) will be described using mean and standard deviation for continuous variables and medians and ranges for discrete variables.

The primary efficacy variable is the change in symptoms at the end of the periods of PMA or placebo study drug administration. The p-value, least square (LS) treatment means, difference between the LS treatment means, and 95% confidence intervals for the treatment differences will be presented.

The secondary efficacy variables are rescue medication requirement and adverse events. These changes will be analyzed similarly to that of the primary efficacy variable.

The percentage of subjects stopping PMA or placebo administration due to intolerance or lack of efficacy will be summarized by treatment group, and the groups will be compared using Fisher's exact test.

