### **8.2 Monitoring Subject Treatment Compliance**

Study subject compliance will be monitored by the accuracy of their attendance at the study site for their bi-weekly immunotherapy treatments. If a subject is persistently noncompliant with the follow up clinic visits for immunotherapy, it may be appropriate to withdraw the subject from the

study. All subjects should be re instructed about the essentiality of scheduled clinic follow-up visits for immunotherapy during each of their scheduled clinic visits.

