- If the subject experiences a worsening or complication of an AE after any change in study medication, the worsening or complication should be recorded as a new AE. Investigators should ensure that the AE term recorded captures the change in the condition (eg, “worsening of...”).

Changes in severity of AEs /Serious PTEs:

- If the subject experiences changes in severity of an AE/serious PTE, the event should be captured once with the maximum severity recorded.

Preplanned surgeries or procedures:

- Preplanned procedures (surgeries or therapies) that were scheduled prior to signing of informed consent are not considered PTEs or AEs. However, if a preplanned procedure is performed early (eg, as an emergency) due to a worsening of the pre-existing condition, the worsening of the condition should be captured appropriately as a PTE or an AE. Complications resulting from any planned surgery should be reported as AEs.

Elective surgeries or procedures:

- Elective procedures performed where there is no change in the subject’s medical condition should not be recorded as PTEs or AEs, but should be documented in the subject’s source documents. Complications resulting from an elective surgery should be reported as AEs.

Insufficient clinical response (lack of efficacy):

- Insufficient clinical response, efficacy, or pharmacologic action, should NOT be recorded as an AE. The investigator must make the distinction between exacerbation of pre-existing illness and lack of therapeutic efficacy.

Overdose:

- Cases of overdose with the immunotherapy without manifested side effects are NOT considered PTEs or AEs, but instead will be documented on an Overdose page of the CRF. Any manifested side effects will be considered PTEs or AEs and will be recorded on the AE page of the CRF.

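### The synopsis plans a test on stops for intolerance or lack of efficacy, but the reason list in 6.4 has no lack-of-efficacy code, so that part of the count is at risk of being too low

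*Combined protocol and SAP*

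**What the plan says.** The protocol synopsis, under Statistical Considerations (Efficacy Analyses), plans a by-reason comparison: "The percentage of subjects stopping PMA or placebo administration due to intolerance or lack of efficacy will be summarized by treatment group". On the method, the same sentence says that "the groups will be compared using Fisher's exact test". That sentence does not state sidedness; the default in section 12.1.1 is two-sided at 0.05.

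Section 6.4 governs how the reason is captured: "The primary reason for discontinuation or withdrawal of the subject from the study or study medication should be recorded in the CRF using the following". The seven categories are:

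1. pretreatment event or adverse event
2. significant protocol deviation
3. lost to follow-up
4. voluntary withdrawal
5. study termination
6. pregnancy
7. unacceptable risk as judged by the investigator

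Category 1 includes the case where "the subject is unwilling to continue because of the PTE or AE". Under category 4 the site is told: "All attempts should be made to determine the underlying reason for the withdrawal and, where possible, the primary underlying reason should be recorded".

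Section 9.1.3 adds: "Insufficient clinical response, efficacy, or pharmacologic action, should NOT be recorded as an AE".

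The SAP has no by-reason comparison. Under Other Comparisons and Outcomes it plans: "Comparison of the drop out rates between both groups I and II using a one-tailed Fischer's exact test". Protocol section 12.1.3 likewise compares overall drop-out only.

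**The concern.** The planned numerator has two components, and the data collection gives a code to only one. Intolerance maps to category 1. Lack of efficacy maps to nothing: it is not on the list, there is no residual category (the screen-failure list in 8.1.11 has one), and 9.1.3 closes the adverse-event route.

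An analyst working from the coded primary reason would therefore report intolerance stops under a label that promises intolerance or lack of efficacy. If lack-of-efficacy stops differ between arms, the comparison would miss that difference to the extent that the stops sit uncounted under another code. A reason not captured when the subject stops may not be recoverable later.

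**Working it through.** The plan states no figure for stops by reason, so there is nothing to reproduce for this test. The nearest figure is the drop-off allowance in section 12.3: 36 − 28 = 8 subjects, or 8/36 = 22.2%, for all causes. At 1:1 allocation, 36 subjects give 18 per arm.

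**Step 1: trace each kind of stop through 6.4.**

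| Why the subject stops | Coded reason available in 6.4 | In the synopsis numerator? |
|---|---|---|
| Intolerance | Category 1 (adverse event) | Yes, from the code |
| Lack of efficacy, and wishes to leave the study | Category 4 (voluntary withdrawal) is the natural home | Only if the underlying reason is obtained, recorded and then used |
| Lack of efficacy, stops injections but stays for follow-up | None: category 4 is framed as a wish to leave the study, although 6.4 says it also covers stopping study medication | Not from any code |

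The entry under category 4 is conditional (the reason if provided, the primary underlying reason where possible). No text says how it becomes a countable category or that the synopsis test will use it.

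**Step 2: check for a fallback.** Section 12.1.3 and the SAP compare all drop-out regardless of reason. They need no reason codes and are unaffected, but they do not answer the by-reason question.

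**Step 3: show the range with assumed counts.** Assume 8 subjects stop for intolerance or lack of efficacy, equal to the drop-off allowance: 1 active (intolerance) and 7 placebo (1 intolerance, 6 lack of efficacy). These counts are not in the documents. The two-sided Fisher's exact test at 18 per arm gives:

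| Placebo lack-of-efficacy stops not counted | Active vs placebo | p |
|---|---|---|
| 0 | 1/18 vs 7/18 | 0.041 |
| 1 | 1/18 vs 6/18 | 0.088 |
| 2 | 1/18 vs 5/18 | 0.18 |
| 3 | 1/18 vs 4/18 | 0.34 |
| 6 (all) | 1/18 vs 1/18 | 1.00 |

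If every underlying reason is captured and used, the first row stands and nothing is lost.

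**Step 4: test how far the illustration depends on the split.** With 5 lack-of-efficacy stops on placebo, none on active and no intolerance stops, full counting gives 0/18 vs 5/18, p = 0.045. The planned test is on the composite, however. Adding 1 or 2 intolerance stops on active gives 1/18 vs 5/18, p = 0.18, or 2/18 vs 5/18, p = 0.40. Even with perfect coding, a significant composite result may not exist to be lost.

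**The case against.** The strongest reply is that these stops are not necessarily lost. Category 4 tells sites to make every attempt to find the underlying reason, and section 12.1 already plans a blind data review at which recorded reasons could be classified before unblinding. A reader might infer from the missing code that lack-of-efficacy stops will certainly be miscounted. The documents do not support that; they support a risk of undercounting.

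A reader might also infer that the gap hides a benefit of PMA, because section 12.3 assumes 80% efficacy on active and 30% on placebo. Those are response rates, not stopping rates. Subjects with uncontrolled symptoms are offered stepwise rescue medication (Appendix I), which gives them an alternative to stopping. Nor can intolerance be presumed to fall mainly on active: histamine is added to placebo and is expected to cause mild itch in about 20% of controls, against local reactions in up to 20% on active. The direction of any distortion is unknown.

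Two further replies hold. The 9.1.3 rule is not itself a fault; it only closes category 1 as a route. And the End of Study CRF page is not shown, so it may have a reason field that cannot be checked here.

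It is also tempting to list the withdrawal for missed visits in 8.2 as ordered by the protocol but lacking a code. That section is discretionary: "If a subject is persistently noncompliant with the follow up clinic visits for immunotherapy, it may be appropriate to withdraw the subject". Withdrawal after unblinding (7.3) is mandatory and has no dedicated code, but neither case bears on this Fisher test.

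The mismatch itself survives. The synopsis names a reason that the 6.4 list cannot record as a code, and the free-text route has no stated rule for turning it into a count.

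**Conclusion.** The point holds as a minor gap between data collection and a planned analysis. The lack-of-efficacy part of the synopsis numerator cannot be formed from the coded primary reason and is at risk of undercounting. A subject who stops injections for lack of effect but does not wish to leave the study fits no category.

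The size cannot be computed from the documents. It runs from none to complete loss of the lack-of-efficacy component, and the p-values shown rest entirely on assumed counts. The by-reason test is in the synopsis only. The overall drop-out comparison does not depend on reason codes, and the primary outcomes (DCS and mini-RQLQ), TNSS and the adverse-event comparison are not affected.

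**What to change.** 1. Add 'Lack of efficacy' and 'Other (specify)' to the primary-reason list in 6.4 and to the End of Study CRF page, and make clear that the list applies to stopping injections as well as to leaving the study.
2. Define the numerator of the synopsis comparison as stops coded as pretreatment/adverse event or as lack of efficacy. Report the two components separately as well as combined. Classify any free-text reasons at the blind data review in section 12.1.
3. Decide whether the test is still planned. If so, carry it into section 12.1.3 and the SAP with its sidedness stated; if not, delete it from the synopsis.
4. Optionally, add codes for withdrawal after unblinding (7.3) and for discretionary withdrawal for noncompliance (8.2).

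The cost is a few tick-boxes on a paper CRF and short text edits in 6.4, section 12.1.3 and the SAP. No extra visits or subjects are needed.
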